8.5.4 Evaluation of Weight Loss

Maximum percent change from baseline in weight, with weight loss > 8%, >9%, and >12% will be summarized, including a breakdown by age, gender, baseline BMI, by use of AChEI, and by disease severity at baseline (MMSE ≤ 26 , MMSE > 26).

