# Safety Data

The combined safety data of both tramiprosate Phase 3 studies includes 2025 subjects treated for up to 78 weeks, and approximately 400 treated up to 130 weeks, and suggests a favorable long term safety profile. In the overall safety population, the most common AEs with incidence > 2 × placebo rates were nausea, vomiting, and weight loss [Abushakra et al. 2016]. The safety profile was similar in the APOE4/4 subjects [Abushakra et al. 2017]. There was a low incidence of serious adverse events (SAEs) leading to withdrawal. Most TEAEs were mild to moderate in severity.

An important safety advantage of tramiprosate was that no cases of ARIA-E (vasogenic edema) were detected by central MRI assessments of 426 AD subjects, including APOE4 carriers [Abushakra et al. 2016].

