# 2.4. Potential Risks and Benefits

Tramiprosate, the active agent of ALZ-801, has been studied in 3295 adults across 16 clinical studies, including 2800 AD subjects. The Phase 3 studies included 2025 subjects treated for up to 78 weeks, of whom 714 subjects were treated for up to 52 additional weeks in an extension study. Therefore, a total of 371 AD subjects received tramiprosate for up to 2.5 years. In the controlled Phase 3 studies, the most common AEs showing dose-dependence were GI in nature and included nausea, vomiting, and weight loss. Nausea and vomiting were mostly mild to moderate, led to low number of withdrawals, and likely represent local effects of tramiprosate on the GI mucosa.

In the safety extension study, the most common AEs were falls, nausea, urinary tract infection, and diarrhea; typically seen in AD studies. There was no organ toxicity with long-term treatment.

The other AEs were representative of the comorbidities seen in this population and, therefore, no specific risks were identified. The AE profile seemed similar among the APOE4 non-carriers and the APOE4 heterozygous and APOE4/4 homozygous subgroups.

Central brain MRI assessments from 426 subjects in the tramiprosate Phase 3 studies, of whom 254 were APO4 carriers, showed no occurrence of vasogenic edema (ARIA-E) on active drug.

The benefits seen in APOE4/4 subjects with Mild AD include lesser decline in cognition and function over 78 weeks, and lower disability scores. These effects were demonstrated in subjects already receiving maximum standard of care; therefore, representing additional benefits of tramiprosate treatment.

Safety data from the ALZ-801 Phase 1 program which included AD patients and healthy volunteers supports improved GI tolerability especially when taken with food. This protocol requires that ALZ-801 be taken with or within 30 minutes after food.

Based on the promising efficacy in APOE4/4 subjects and the favorable safety profile in all subjects including APOE4 carriers, tramiprosate seems to provide a favorable benefit risk profile in subjects with Mild or Early AD. ALZ-801 at a dose of 265mg BID will provide equivalent

Confidential Page 36 of 115

exposures to tramiprosate 150mg BID, and is expected to provide a favorable benefit-risk profile in APOE4/4 homozygotes with AD.

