- Subject with confirmed clinically notable changes in liver function tests (LFT) may be withdrawn from the study. The criteria for abnormal LFTs are as follows:
  - $\circ$  ALT or AST  $> 8 \times ULN$ ,
  - $\circ$  ALT or AST  $> 5 \times$  ULN for more than 2 weeks, or
  - o ALT or AST  $> 3 \times$  ULN, and TBL  $> 2 \times$  ULN or PT  $> 1.5 \times$  ULN
- Weight loss: Subjects who are not intentionally dieting who show the following degree of weight loss on study drug:
  - $\circ$  Weight loss > 6% of body weight compared to baseline, and
  - Reaching BMI < 22 if  $\ge$  65 years of age; or
  - o Reaching BMI < 16 if < 65 years of age

**Note**: The ideal body weight and BMI cut-off criteria for those < 65 years of age or  $\ge 65$  years of age are based on a meta-analysis by Winter et al. (2017).

The reason for discontinuation must be recorded on the appropriate page of the electronic case report form (eCRF).

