#### 10.10.6. Physical Examination

The number and percentage of subjects with abnormal physical examination findings will be summarized. Analyses of subjects with weight loss of > 6% from baseline will be provided for subjects with weight loss without intentional dieting.

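### SAP 8.5.4 does not produce the >6% weight-loss analysis in non-dieting subjects that Protocol 10.10.6 promises, and gives no reason

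*SAP*

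**What the plan says.** **Promised analysis.** Protocol 10.10.6 (Physical Examination) states: "Analyses of subjects with weight loss of > 6% from baseline will be provided for subjects with weight loss without intentional dieting".

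**Withdrawal criterion.** Protocol 5.5 uses the same figure for subjects who are not intentionally dieting: "Weight loss > 6% of body weight compared to baseline, and" a BMI limit that depends on age. The limit is below 22 from age 65 upward. For younger subjects it reads "Reaching BMI < 16 if < 65 years of age".

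**Planned analysis.** SAP 8.5.4 takes the maximum percent change in weight, "with weight loss > 8%, >9%, and >12% will be summarized", broken down by age, gender, baseline BMI, AChEI use and MMSE group. SAP 8.5.5 adds weight by visit as change and percent change. Table 17 of the SAP has no weight row, and the SAP does not mention intentional dieting.

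**Why weight is of interest.** Protocol 2.4 says of the controlled tramiprosate Phase 3 studies that "the most common AEs showing dose-dependence were GI in nature and included nausea, vomiting, and weight loss". Protocol 2.3.1.1 (Safety Data) adds that in the overall safety population "the most common AEs with incidence > 2 × placebo rates were nausea, vomiting, and weight loss".

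**The concern.** The protocol names one weight-loss cut for analysis, and the SAP's three cuts all lie above it. The restriction to unintentional loss has gone too. This is the protocol's only specific commitment for analysing weight loss. Safety and tolerability is a primary objective, and Protocol 4.2.1 lists body weight among the safety endpoints.

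At stake is a simple comparison between arms: how many subjects lost more than 6%, and how many met the protocol's own weight criterion for withdrawal. As the SAP stands, neither count is planned as a table.

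**Working it through.** There is no stated figure to reproduce. The check is a comparison of text, followed by arithmetic on the protocol's own limits.

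**1. Promise against plan**

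| Item | Protocol 10.10.6 | SAP 8.5.4 |
|---|---|---|
| Lowest cut | >6% | >8% |
| Other cuts | none | >9%, >12% |
| Restricted to unintentional loss | yes | no |
| Reason for the difference | n/a | none given |

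The SAP carries other protocol safety thresholds over unchanged: liver tests (Protocol 10.10.2), ECG intervals (Protocol Table 5) and vital signs (Protocol Table 4, SAP Table 17). SAP section 5 also explains its larger departures from Protocol version 3.0, namely the DAD, imaging and fluid biomarker changes. The weight cuts differ without comment.

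**2. Where the withdrawal criterion falls relative to 8%**

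I read Protocol 5.5 as requiring both a loss above 6% and a BMI below the limit for the subject's age. After a fractional loss L, BMI equals baseline BMI × (1 − L). The limit is therefore crossed at loss L when baseline BMI is below limit / (1 − L).

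| Age | BMI limit | Met as soon as loss passes 6% if baseline BMI is below | Met before 8% loss if baseline BMI is below |
|---|---|---|---|
| 65 or over | 22 | 22/0.94 = 23.40 | 22/0.92 = 23.91 |
| Under 65 | 16 | 16/0.94 = 17.02 | 16/0.92 = 17.39 |

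Entry BMI runs from 17 to 40 (inclusion criterion 11), so the younger group is affected only at the very bottom of the range. In the older group, any eligible subject with baseline BMI below about 23.9 can meet the criterion somewhere between 6% and 8% loss.

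**3. Whether such a subject could still reach the 8% category later**

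The early termination visit records weight. The retrieved-dropout visits (Protocol 7.2.15) list vital signs but not weight, and Protocol 7.1.10.5 defines vital signs as blood pressure, pulse, respiratory rate and temperature. A subject withdrawn at 6% to 8% may therefore supply no later weight and stay below the SAP's lowest cut. The breakdown by baseline BMI in SAP 8.5.4 does not recover such subjects, because it uses the same cuts.

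**4. Illustration of size (assumed inputs)**

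The documents give no mean or SD for weight change. Suppose percent change is normal with mean 0 to −3% and SD 4% to 7%, and take 325 randomized subjects as about 162 per arm.

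- Mean 0, SD 4: P(loss >6%) = 0.067 and P(loss >8%) = 0.023. The band holds 0.044 × 162 = 7.1 subjects per arm, which is 0.044/0.067 = 66% of those losing more than 6%.
- Mean −3, SD 4: 0.227 and 0.106. The band holds 0.121 × 162 = 19.6 subjects per arm.
- Mean −3, SD 7: 0.334 and 0.238. The band is 0.096/0.334 = 29% of those losing more than 6%.

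Over this grid the 6% to 8% band holds about 7 to 20 subjects per arm, or 29% to 66% of all subjects losing more than 6%. The figures use one distribution for both arms, treat change as a single measurement although SAP 8.5.4 uses the maximum, and include dieters. They say nothing about a difference between arms.

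**The case against.** The strongest reply is that weight is well covered without a 6% row. A loss of 6% to 8% contributes to the maximum and by-visit percent change summaries (SAP 8.5.4, 8.5.5). Weight loss reported as an adverse event appears by arm in the tables of SAP 8.5.2, and the earlier tramiprosate signal was itself reported as adverse event incidence. Reasons for early termination are summarized (SAP 7.1) and all CRF data are listed (SAP 8.1), so a >6% count can be derived. Safety analysis is descriptive, and no test or efficacy conclusion changes. All of this stands, and it limits the point to a missing tabulation.

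It also rules out some stronger readings:

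- A reader might infer that 6% is the protocol's withdrawal threshold. It is one component of a joint criterion, so a plain >6% row would not give the rate of subjects meeting Protocol 5.5.
- A reader might infer that losses of 6% to 8% go uncounted or that a signal is hidden. The summaries just listed contradict that.
- A reader might infer a known dose-related effect of ALZ-801. The statements in Protocol 2.4 and 2.3.1.1 concern tramiprosate in earlier trials.
- A reader might call the closeness of the 8% and 9% cuts an error. It conflicts with nothing in the documents.

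What the reply does not answer is why a specific protocol commitment was dropped without explanation. A count that someone could derive from listings is not a planned comparison by arm.

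**Conclusion.** The mismatch holds: the >6% analysis in subjects not intentionally dieting has no counterpart in the SAP and no reason is given. The consequence is modest. One committed between-arm tabulation is missing for an effect that the protocol links to the active moiety, and the lowest SAP category can miss subjects aged 65 or over with baseline BMI below about 23.9 who meet the withdrawal criterion before 8% loss.

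The BMI result follows from the protocol's own limits, provided that the criterion is read as joint. The number of subjects affected is unknown, and the range of 7 to 20 per arm is illustration only. No design figure, test or error rate changes. I take no position on which clinical threshold is right, only that the passages must be reconciled.

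**What to change.** Reconcile SAP 8.5.4 with Protocol 10.10.6:

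- Add a >6% category by arm to the existing table for all subjects, and again excluding intentional dieting where dieting status is recorded. The overall row goes beyond what the protocol promises, but it makes the new cut comparable with the existing ones.
- Add a count by arm of subjects meeting the full weight criterion of Protocol 5.5, that is, the weight and BMI components together in subjects not intentionally dieting. State which age and height enter the derivation.
- If the sponsor prefers the present cuts, state and justify the departure in the SAP, as was done for the other changes from Protocol version 3.0.

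The cost is a table row and a derived flag with age-specific BMI logic. The overall row needs only collected weights. The non-dieting row and the full flag also need dieting status. The protocol's visit procedures do not show a field for it, so the sponsor should confirm that it is captured. If it is not, the SAP should say so and define how unintentional loss will be identified, for example by blinded case review before database lock.

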8.5.5 Evaluation of Electrocardiogram (ECG) Findings

Electrocardiogram (ECG) Findings

Electrocardiograms will be assessed by a central reader and will be recorded at the following visits:

- Screening/Visit 1
- Visit 4/Day 43
- Visit 5/Day 92

- Visit 7/Week 26
- Visit 9/Week 52
- Visit 11/Week 78

The following quantitative parameters will be reported by the central reader: heart rate, PR interval, QRS duration, QT interval (uncorrected), and QT interval with Fridericia's correction (QTcF). Change from baseline and percent change from baseline by visits will be calculated for each parameter. The number and percent of patients within each category (normal, abnormal not clinically significant, and abnormal clinically significant) will also be summarized by visit. A standard triplicate 12-lead ECG will be performed at the Screening, Visit 4 and Visit 5. At subsequent visits, a single 12-lead ECG will be performed unless there is evidence of QT prolongation, in which case a triplicate ECG must be performed. Assessment of clinically notable abnormalities will be based on the average of triplicate ECG readings. To be conservative, the worst interpretation of the three readings will be used to generate the summary of ECG clinically notable abnormalities table. The denominator for the percentages will be the number of patients with a result at the specific visits for each parameter.

Clinically notable changes in ECGs will be listed for individual study subjects and tabular summaries provided per visit. The criteria for clinically significant ECGs results are as follows:

- PR interval \geq 220 msec
- PR interval ≤ 120 msec
- QRS duration ≥ 120 msec and increase of ≥ 20 msec from baseline
- OT interval >500 msec
- QTcF interval > 500 msec and increase of ≥ 60 msec from baseline

Categorical Analyses of QTcF Interval

At each visit with ECG, observed QTcF data will be summarized into the following categories and shift tables provided:

- Categories of QTcF \leq 450msec, 451-480 msec, 481-500 msec, and \geq 500 msec
- Categories of QTcF > 450 msec, > 480 msec, and > 500 msec
- Categories of CBL in QTcF: ≤ 10 msec, 11-30 msec, 31-60 msec
- Categories of CBL in QTcF: > 30 msec, > 60 msec

Vital Signs

Vital signs will be assessed at all visits except Visit 3 and Visit 6. The following parameters will be summarized: systolic blood pressure (SBP), diastolic blood pressure (DBP), body

temperature and respiratory rate. Weight and Height will also be summarized for available visits. These parameters will be summarized through change from baseline and percent change from baseline in similar fashion as the ECG parameters.

Vital signs will be assessed through potentially clinically significant (PCS) criteria. Patients will be counted if they meet the criteria at any time post-baseline. The denominator for the percentages will be the number of patients with a result at the specific visits for each parameter.

Clinically notable systolic and diastolic BP will be listed for individual subjects and summarized using descriptive statistics. Clinically notable criteria are described in Table 17.

 Table 17 Criteria for Clinically Notable Vital Sign Abnormalities

Parameter	High Threshold	Low Threshold
Systolic BP	> 30 mm Hg increase from baseline	> 30 mm Hg decrease from baseline
Diastolic BP	> 20 mm Hg increase from baseline	> 20 mm Hg decrease from baseline
Pulse rate	> 120 beats/min and an increase in pulse rate of ≥ 15 beats/min from baseline	< 40 beats/min and a decrease in pulse rate of \geq 15 beats/min from baseline
Body	> 39.0°C (≥ 102.2°F)	< 35.0°C (≤ 95.0°F)
temperature		

BP: blood pressure

Physical Examinations

Physical examinations will be performed at all visits except Visit 3 and Visit 6. All data will be listed. The number and percentage of subjects with abnormal neurological examination findings will be summarized.

Neurological Examinations

Neurological exam will be performed at the following visits:

- Screening/Visit 1
- Visit 7/Week 26
- Visit 9/Week 52
- Visit 11/Week 78
- Safety Follow up Visit/Week 82

All data will be listed. The number and percentage of subjects with abnormal neurological examination findings will be summarized.

8.5.6 Other Safety Analyses

C-SSRS suicidal behavior, suicidal ideation, and intensity of most severe ideation will be listed and summarized by visit and by questionnaire types (baseline and since last visit). The number and percentage of subjects with abnormal C-SSRS scores will be summarized.

9 INTERIM ANALYSIS

No interim analyses are planned or were conducted.

10 STATISTICAL SOFTWARE

All analyses will be performed using SAS Version 9.4.

12 APPENDICES

Appendix 1 Schedule of Evaluation (Protocol v3.0)

	Screening*			Double-Blind Treatment										
Visit (V)	V 1a	V 1b	V 2	V 3	V 4	V 5	V 6	V 7	V 8	V 9	V 10	V 11	ET	Safety FU
				Phone			Phone					EOT		EOS
Visit Time	Scr – Part 1	Scr –	#Bsl	W 2	W 6	W 13	W 20	W 26	W 39	W 52	W65	W 78	TBD	W 82
		Part 2	Day1	Day15	Day43	Day92			Day274		Day456	Day547		Day574
Window	Up to -13 weeks	_	_	± 2 d	±7 d	± 14 d	± 2 d	± 14 d	_	±7 d				
Informed consent/ caregiver/study partner consent ¹	X	X												
MMSE Score	X		X			X		X	X	X	X	X	X	
Prohibited medications	X													
Demographics, medical history	X													
APOE testing	X													
Vital signs ²		X	X		X	X		X	X	X	X	X	X	X
Physical examination		X	X		X	X		X	X	X	X	X	X	X
Neurological examination		X						X		X		X	X	X
Height		X												
Weight		X	X		X	X		X	X	X	X	X	X	X
Prior/concomitant medications		X	X	X	X	X	X	X	X	X	X	X	X	X
AD diagnostic criteria		X												
RBANS		X												
Evidence of progressive memory loss over the last 12 months		X												
12-Lead ECG ³		X			X	X		X		X		X	X	
Future potential genomic testing		X												
Safety lab tests ⁴		X			X	X		X	X	X	X	X	X	
Serum FSH/hCG test ⁵		X												
Immunology (HIV, Hep B S Ag, Hep C Ab, HCV RNA if applicable)		X												
Urinalysis		X			X	X		X		X		X	X	
Urine Pregnancy test ⁶			X		X	X		X	X	X	X	X	X	
Urine drug screen		X												
Adverse events	X	X	X	X	X	X	X	X	X	X	X	X	X	X
MRI ⁷		X						X		X		X	X	
Inclusion/exclusion criteria			X					1						
Randomization			X											
ADAS-Cog			X			X		X		X		X	X	
A-IADL			X					X		X		X	X	
CDR ⁸		X						X		X		X	X	
DAD			X					X		X		X	X	

	Screenin	Screening*			Double-Blind Treatment										
Visit (V)	V 1a	V 1b	V 2	V 3	V 4	V 5	V 6	V 7	V 8	V 9	V 10	V 11	ET	Safety FU	
				Phone			Phone					EOT		EOS	
Visit Time	Scr – Part 1	Scr –	#Bsl	W 2	W 6	W 13	W 20	W 26	W 39	W 52	W65	W 78	TBD	W 82	
		Part 2	Day1	Day15	Day43	Day92	Day141	Day183	Day274	Day365	Day456	Day547	100	Day574	
Window	Up to -13 weeks	_	_	± 2 d	$\pm 7 d$	± 14 d	± 2 d	± 14 d	± 14 d	± 14 d	$\pm 14 d$	± 14 d	_	$\pm 7 d$	
NPI			X					X		X		X	X		
QoL-AD			X							X		X	X		
RUD Lite			X							X		X	X		
C-SSRS ⁹		X	X		X	X		X	X	X	X	X	X	X	
CSF sampling ¹⁰			X							X		X	X		
Plasma biomarkers			X		X	X		X	X	X	X	X	X		
PK sample collection ¹¹			X		X	X		X	X	X	X	X	X		
Time of last dose prior to clinic visit					X	X		X	X	X	X	X	X		
Study drug return, accountability, compliance					X	X		X	X	X	X	X	X		
Study drug dosing on site ¹²			X		X	X		X	X	X	X	X			
Dispense study drug ¹³			X		X	X		X	X	X	X				

ADAS-Cog: Alzheimer's Disease Assessment Scale – cognitive subscale; A-IADL: Amsterdam Instrumental Activities of Daily Living; APOE: apolipoprotein E; BP: blood pressure; Bsl: baseline; CDR: Clinical Dementia Rating; CSF: cerebrospinal fluid; C-SSRS: Columbia-Suicide Severity Rating Scale; CT: computed tomography; d: Day; DAD: Disability Assessment for Dementia; ECG: electrocardiogram; EOS: end of study; EOT: end of treatment; ET: early termination; FSH: follicle-stimulating hormone; FU: Follow-up; hCG: human chorionic gonadotropin; HCV RNA: hepatitis C virus RNA; Hep B S Ag: hepatitis B surface antigen; Hep C Ab: hepatitis C antibody; HIV: human immunodeficiency virus; LP: lumbar puncture; MMSE: Mini-Mental State Examination; MRI: magnetic resonance imaging; NPI: Neuropsychiatric Inventory; PK: pharmacokinetics; QoL-AD: Quality of Life in Alzheimer's Disease; QTc: corrected QT (interval); Scr: Screen; RBANS: Repeatable Battery for the Assessment of Neuropsychological Status; RUD Lite: Resource Utilization in Dementia Lite version; TBD: to be determined; V: visit; W: week.

- * Previous evidence of APOE4/4 status may be used as a reference and allow subjects to combine Screening Par 1 Visit and Screening Part 2 Visit together at the same day if the site and subject prefer. Screening procedures may be conducted over several visits during the Screening period provided that the results are available to evaluate inclusion and exclusion criteria before randomization.
- 1. Informed consent at Screening Part 1 Visit is for APOE genotyping, MMSE, demographics, medical history and prohibited medications. Complete consent from subject and caregiver/study partner at the Screening Part 2 Visit or at the Screening Part 1 Visit if APOE4/4 status is known or confirmed using a rapid genotype test.
- 2. Vital sign measurements (BP, pulse, respiratory rate, and body temperature) will occur prior to dosing, LP, and blood draw, where applicable. BP and pulse will be measured after the subject has been sitting for 5 minutes. All BP measurements should be performed on the same arm, preferably by the same person, using an inflatable cuff and calibrated manometer. After last blood collections, subjects will be observed for approximately 15 minutes. BP and pulse while sitting will be measured and documented at the end of this observation period.
- 3. ECGs should be obtained after the subject has rested quietly in the supine position for at least 5 minutes. Triplicate ECG will be performed at screening, Week 6, and Week 13. Triplicate ECG at Week 26, Week 78, and ET will be performed only if QTc prolongation observed in current and prior visits.
- 4. Lab tests include clinical chemistry, hematology, and coagulation tests, and will be done after ADAS-Cog and CDR-SB assessments.
- 5. Serum FSH levels will be measured only for female subjects of non-childbearing potential. Serum hCG levels will be measured only for female subjects of childbearing potential.
- 6. Urine pregnancy tests will be conducted only for female subjects of childbearing potential.
- 7. For those who cannot undergo MRI, CT is acceptable at Screening but requires prior approval by Medical Monitor. These subjects will not be scheduled for further CT imaging and will not contribute to the assessment of the volumetric imaging biomarkers. Note: CT is not allowed for subjects of sites at Germany.
- 8. At screening, CDR global score and memory box score are calculated for screening purposes; the sum of boxes score is recorded at subsequent visits.
- 9. C-SSRS: B/S = baseline/screening version, SLV = since last visit version.
- 10. This CSF sub-study intends to enroll 60 subjects per treatment group. For each subject, LP will be performed within the same 2-hour window on each of the 3 visits regardless of dosing time and other assessments. In other words, for any two of the three CSF collections, the maximal time difference, in terms of the time of day, is within 2 hours from each other. Time of CSF collection (not time of preparation) will be recorded.
- 11. Plasma PK samples will be collected at pre-dose at each clinic visit. Additional, a PK sample at ≥ 1 hour post-dose during clinic visit will be collected at Week 65.
- 12. The times of study drug administration when taken at the study site will be recorded.
- 13. Last study drug administration will occur on the morning of the Week 78 visit. One dose is administered at the site during clinic visits; the evening dose is skipped on clinic visit days. #Baseline MMSE used for change from baseline analyses will be the average of V1a and V2 scores.
